7. PRIMARY STATISTICAL ANALYSES

7.1. Primary Efficacy Analyses

7.1.1. Overview of Planned Primary Efficacy Analyses

The primary efficacy analyses will be based on the Modified Intent-To-Treat population, for the analysis on all countries overall and on China Modified Intent-To-Treat population for the analysis on China subgroup alone, unless otherwise specified.

Table 3 provides an overview of the planned efficacy analyses, with full details of data displays being presented in [Appendix 14: List of Data Displays](#). All the planned primary efficacy analyses will be done on all countries overall, and China subgroup alone (with the exception of those displays specified by country).

Table 3 Overview of Planned Efficacy Analyses

| Endpoints | Absolute | | | | | | Change from Baseline | | | | | | | |
|---|------------------|---|---|------------------|---|------------|----------------------|------------------|---|---|------------------|---|------------|---|
| | Stats Analysis | | | Summary | | Individual | | Stats Analysis | | | Summary | | Individual | |
| | T | F | L | T | F | F | L | T | F | L | T | F | F | L |
| Primary Efficacy Analyses | | | | | | | | | | | | | | |
| Baseline FEV ₁ | | | | Y ^[1] | | | Y | | | | | | | |
| Trough FEV ₁ on Day 169 | Y ^[1] | | | Y ^[1] | | | Y | Y ^[1] | Y | | Y ^[1] | Y | | |
| Trough FEV ₁ on Day 169 (Using LOCF) | Y | | | Y | | | Y | | | Y | | | | |
| Trough FEV ₁ at other time points | Y | | | Y | | | Y | Y | Y | | Y | | Y | |

NOTES :

- T = Table, F = Figure, L = Listing, Y = Yes display generated.
- Stats Analysis = Represents TFL related to any formal statistical analyses (i.e. modelling) conducted.
- Summary = Represents TFL related to any summaries (i.e. descriptive statistics) of the observed raw data.
- Individual = Represents FL related to any displays of individual subject observed raw data.
- All the tables will be presented by treatment group.

[1]: Will be repeated for PP population.

7.1.2. Planned Primary Efficacy Statistical Analyses

| Primary Statistical Analyses | |
|---|--|
| Endpoint(s) | |
| 
 Change from baseline in trough FEV1 | |
| Model Specification | |
| 
 Mixed Models Repeated Measures (MMRM) model. While missing data are not explicitly imputed in the primary MMRM analyses, there is an underlying assumption that the data are missing at random. All available scheduled postbaseline assessments will be utilized and via modeling of the within-subject correlation structure, the derived treatment differences will be adjusted to account for missing data. The MMRM analysis for trough FEV1 will include on-treatment FEV1 measurements at Days 2, 28, 56, 84, 112, 168 and 169. Terms fitted the model: 
 Response :trough FEV1 on each day or Change from baseline in trough FEV1 on each Day Categorical :Treatment, Smoking Status (screening), Country^[1], Day Continuous :Baseline FEV1 Interaction : baseline*Day, treatment*Day Repeated : Day (nominal) | |
| 
 The model will be fit with an unstructured variance-covariance matrix. The Kenward and Roger method (KR) for approximating the denominator degrees of freedom and correcting for bias in the estimated variance-covariance of the fixed effects will be used. In the event the model fails to run using the KR method, then the residual method will be used instead. Baseline is defined in Section 10.5.2.1 Two models will be fitted; one with trough FEV1 on each Day and one with Change from baseline in trough FEV1 on each Day. | |
| Model Checking & Diagnostics | |
| 
 Refer to Appendix 12: Model Checking and Diagnostics for Statistical Analyses. | |
| Model Results Presentation | |
| 
 Least-square (LS) means and LS mean change from baseline values for each treatment group will be presented with their associated standard errors. Estimated treatment differences along with corresponding 95 % confidence intervals (CIs) and p-values for Days 2, 28, 56, 84, 112, 168 and 169 will be presented for the treatment comparisons The LS means from the model for change from baseline in trough FEV1 for each treatment on Days 2, 28, 56, 84, 112, 168 and 169, along with the corresponding 95 % CIs, will be plotted. The LS mean treatment differences, along with the corresponding 95 % CIs, for change from baseline in trough FEV1 on Days 2, 28, 56, 84, 112, 168 and 169 will be plotted for active treatment group versus placebo. The type III tests of fixed effects and the covariance parameter estimates from the model will | |

| Primary Statistical Analyses | |
|---|--|
| be presented in two tables in the statistical appendix. | |
| Example SAS Code | |
| proc mixed data=dsetin; | |
| class trtcd visit subjid smk country ^[1] ; | |
| model endpoint=trtcd baseline smk country ^[1] day day*baseline day*trtcd / ddfm =kr; | |
| repeated visit / subject=subjid type=un; | |
| lsmeans trtcd*visit / cl diff e om=OMdset at (baseline)=(&blm.); | |
| ods output lsmeans=lsmeans; | |
| ods output diffs=diffs; | |
| run; | |
| [where OMDset is a dataset with a row for every subject-visit combination that contains all of the covariates and blm is a macro variable containing the mean baseline for the subjects used in the analysis. This is used to derive the LS means using coefficients which are based on the subjects used in the analysis.] | |

Note: [1]: In China subgroup analysis, Country will be removed.

| Sensitivity and Supportive Statistical Analyses | |
|---|--|
| • The summaries, figures and analysis detailed in Section 7.1.1 (Overview of Planned Efficacy Analyses) and above primary statistical analyses, except for the summary figures (box plot and empirical distribution function plot, details please refer to Appendix 14), will be repeated for the PP population for the analysis on all countries overall and on China PP population for the analysis on China subgroup alone as the supportive analysis of primary efficacy analyses. | |
| • An assessment of whether the effect of treatment on trough FEV1 is modified by smoking status at screening, country ^[1] or baseline will be made by fitting separate repeated measures models, identical to the model described in the above primary statistical analyses, but also including additional terms for the treatment by smoking status interaction, treatment by country (for the all countries analysis only) interaction and treatment by baseline interaction respectively. | |
| • Additionally, an assessment will be made of whether the effect of treatment on trough FEV1 is modified by the following factors, | |
| ICS use at screening. Reversibility to salbutamol at screening. Post-salbutamol percent predicted FEV1 at screening | |
| This will be made by fitting separate repeated measures models, identical to the model described in Primary Statistical Analyses of Section 7.1.2 but also including additional terms for the factor and the factor by treatment interaction. | |
| • If any interaction from these analyses is significant at the 10 % level, further investigation and characterisation of the interaction will be undertaken. | |
| • The interaction p-values from these analyses will be included in the statistical appendix. | |

Note: [1]: In China subgroup analysis, Country will be removed.

7.1.3. Planned Missing Data Sensitivity Statistical Analyses for Trough FEV1

Missing Trough FEV1 on Day 169 will be imputed using LOCF. This only include post-baseline measurements at on-treatment scheduled clinic visits.

| Sensitivity Statistical Analyses – LOCF | |
|--|--|
| Endpoint(s) | |
| 
 Change from baseline in trough FEV1 on Day 169 | |
| Model Specification | |
| 
 Analysis of Covariance (ANCOVA) model using LOCF Terms in the model: 
 Response: trough FEV1 or change from baseline in trough FEV1 on Day 169. Categorical: treatment group, smoking status (screening), country^[1] Continuous: baseline FEV1 Baseline is defined in Section 10.5.2.1 Two models will be fitted; one with trough FEV1 on Day 169 and one with Change from baseline in trough FEV1 on Day 169. | |
| Model Results Presentation | |
| 
 Least-square (LS) means and LS mean change from baseline values for treatment group will be presented with their associated standard errors. The estimated treatment difference along with corresponding standard error, 95% CI and p-value will be presented. | |
| Example SAS Code | |
| <pre>proc mixed data=dsetin; class trtcd smk country^[1] ; model endpoint=trtcd baseline smk country^[1] / ddfm =kr; lsmeans trtcd / cl diff e; ods output lsmeans=lsmeans; ods output diffs=diffs; run;</pre> | |

Note: [1]: In China subgroup analysis, Country will be removed.

7.2. Secondary Efficacy Analyses

7.2.1. Overview of Planned Secondary Efficacy Analyses

The secondary efficacy analyses will be based on the Modified Intent-To-Treat population, for the analysis on all countries overall and on China Modified Intent-To-Treat population for the analysis on China subgroup alone, unless otherwise specified.

Table 4 provides an overview of the planned efficacy analyses, with further details of data displays being presented in Appendix 14: List of Data Displays. All the planned secondary efficacy analyses will be done on all countries overall, and China subgroup alone (with the exception of those displays specified by country).

Table 4 Overview of Planned Efficacy Analyses

| Endpoint | Absolute | | | | | | | | Change from Baseline | | | | | | |
|-----------------------------------|----------------|---|---|---------|---|------------|---|---|----------------------|---|---|---------|---|------------|--|
| | Stats Analysis | | | Summary | | Individual | | | Stats Analysis | | | Summary | | Individual | |
| | T | F | L | T | F | F | L | T | F | L | T | F | F | L | |
| 0-6 h Weighted Mean FEV1 on Day 1 | Y | | | Y | | | Y | Y | | | Y | | | Y | |
| Baseline Dyspnea Index (BDI) | | | | Y | | | Y | | | | | | | | |
| Transition Dyspnea Index (TDI) | Y | Y | | Y | | | Y | | | | | | | | |

NOTES :

- T = Table, F = Figure, L = Listing, Y = Yes display generated.
- Stats Analysis = Represents TFL related to any formal statistical analyses (i.e. modelling) conducted.
- Summary = Represents TFL related to any summaries (i.e. descriptive statistics) of the observed raw data.
- Individual = Represents FL related to any displays of individual subject observed raw data.
- All the tables will be presented by treatment group.

7.2.2. Planned Secondary Efficacy Statistical Analyses**7.2.2.1. 0-6 h Weighted Mean FEV1 on Day 1**

| | | | | | | |
|--|--|--|-------------|--|------------|----------------|
| Statistical Analyses | | | | | | |
| Endpoint(s) | | | | | | |
| 
 • 0-6 h Weighted Mean FEV1 | | | | | | |
| Model Specification | | | | | | |
| 
 • ANCOVA Model • The absolute and change from baseline value of 0-6 h weighted mean FEV1 on Day 1 will be analysed. • Terms fitted in the ANCOVA model will be include: 
 
 Response	:Absolute value or change from baseline value of 0-6 h weighted mean FEV1 on Day 1	
 
 Categorical	:Treatment, Smoking Status (Screening), Country^[1]	
 
 Continuous	:Baseline FEV1	
 
 • Baseline is defined in Section 10.5.2.1 • Two models will be fitted; one with a response variable of change from baseline and one with the response variable as absolute value. | Response | :Absolute value or change from baseline value of 0-6 h weighted mean FEV1 on Day 1 | Categorical | :Treatment, Smoking Status (Screening), Country ^[1] | Continuous | :Baseline FEV1 |
| Response | :Absolute value or change from baseline value of 0-6 h weighted mean FEV1 on Day 1 | | | | | |
| Categorical | :Treatment, Smoking Status (Screening), Country ^[1] | | | | | |
| Continuous | :Baseline FEV1 | | | | | |
| Model Checking & Diagnostics | | | | | | |
| 
 • Refer to Appendix 12: Model Checking and Diagnostics for Statistical Analyses. | | | | | | |
| Model Results Presentation | | | | | | |
| 
 • LS mean and LS mean change from baseline values for each treatment group will be presented with their associated standard errors. • Estimated treatment differences along with corresponding 95 % CIs and p-values for Day 1 will be presented for the treatment comparisons. | | | | | | |
| Example SAS Code | | | | | | |
| proc mixed data=dsetin; | | | | | | |

| Statistical Analyses |
|---|
| <pre>class trtcd subjid smk country[1]; model endpoint=trtcd baseline smk country[1] / ddfm =kr; lsmeans trtcd / cl diff e om; ods output lsmeans=lsmeans; ods output diffs=diffs; run;</pre> |

Note: [1]: In China subgroup analysis, Country will be removed.

7.2.2.2. TDI

| Statistical Analyses | | | | | | | | | | |
|---|--|--------------------------------|-------------|--|------------|------------------|-------------|---------------------------------------|----------|-----------------|
| Endpoint(s) | | | | | | | | | | |
| Model Specification | | | | | | | | | | |
| 
 TDI | | | | | | | | | | |
| 
 MMRM The model will use all available TDI focal scores recorded on Days 28, 84 and 168. Terms fitted in the model will be include: 
 
 Response	: TDI focal scores on each day	
 
 Categorical	:Treatment, Smoking Status (screening), Country^[1], Day	
 
 Continuous	:BDI focal score	
 
 Interaction	: BDI focal score *Day, treatment*Day	
 
 Repeated	: Day (nominal)	
 
 | Response | : TDI focal scores on each day | Categorical | :Treatment, Smoking Status (screening), Country ^[1] , Day | Continuous | :BDI focal score | Interaction | : BDI focal score *Day, treatment*Day | Repeated | : Day (nominal) |
| Response | : TDI focal scores on each day | | | | | | | | | |
| Categorical | :Treatment, Smoking Status (screening), Country ^[1] , Day | | | | | | | | | |
| Continuous | :BDI focal score | | | | | | | | | |
| Interaction | : BDI focal score *Day, treatment*Day | | | | | | | | | |
| Repeated | : Day (nominal) | | | | | | | | | |
| Model Checking & Diagnostics | | | | | | | | | | |
| 
 Refer to Appendix 12: Model Checking and Diagnostics for Statistical Analyses. | | | | | | | | | | |
| Model Results Presentation | | | | | | | | | | |
| 
 LS means values for each treatment group will be presented with their associated standard errors. Estimated treatment differences along with corresponding 95 % CIs and p-values for Days 28, 84 and 168 will be presented for the treatment comparisons. The LS means from the model for TDI focal score for Days 28, 84 and 168, along with the corresponding 95 % CIs, will be plotted 
 ✓ The LS mean treatment differences, along with the corresponding 95 % CIs for Days 28, 84 and 168 will be plotted for active treatment group versus placebo | | | | | | | | | | |
| Example SAS Code | | | | | | | | | | |
| Similar like the code in Section 7.1.2 . | | | | | | | | | | |

7.3. Other Efficacy Analyses

7.3.1. Overview of Planned Other Efficacy Analyses

Other efficacy analyses will be based on the Modified Intent-To-Treat population, for the analysis on all countries overall and on China Modified Intent-To-Treat population for the analysis on China subgroup alone, unless otherwise specified.

Table 5 provides an overview of the planned other efficacy analyses, with further details of data displays being presented in [Appendix 14: List of Data Displays](#). All the planned study population analyses will be done on all countries overall, and China subgroup alone (with the exception of those displays specified by country).

Table 5 Overview of Planned Other Efficacy Analyses

| Endpoint | Absolute | | | | | | | | Change from Baseline | | | | | | | |
|---|----------------|---|---|---------|---|------------|---|---|----------------------|---|---|---------|---|------------|--|--|
| | Stats Analysis | | | Summary | | Individual | | | Stats Analysis | | | Summary | | Individual | | |
| | T | F | L | T | F | F | L | T | F | L | T | F | F | L | | |
| Time to Onset (an increase of 100mL in FEV1 above baseline) during 0-6 h post-dose on Day 1 | Y | Y | | Y | | | Y | | | | | | | | | |
| Proportion Achieving Increase in FEV1 of $\geq 12\%$ and ≥ 200 mL above Baseline at any Time During 0-6 h Post-dose on Day 1 | Y | | | Y | | | Y | | | | | | | | | |
| Proportion Achieving Increase of ≥ 100 mL above Baseline in Trough FEV1 | Y | | | Y | | | Y | | | | | | | | | |
| Serial FEV1 | Y | Y | | Y | | | Y | Y | Y | | Y | | | | | |
| Trough FVC | Y | | | Y | | | Y | Y | Y | | Y | | | | | |
| Serial FVC | Y | Y | | Y | | | Y | Y | Y | | Y | | | | | |
| Rescue Salbutamol Use (Percentage of Rescue-Free Days) ^[1] | | | | Y | | | Y | | | | Y | | | | | |
| Rescue Salbutamol Use (mean puffs/days) ^[1] | Y | | | Y | | | Y | Y | | | Y | | | Y | | |
| Proportion of Responders According to TDI Focal Score ^[2] | Y | | | Y | | | Y | | | | | | | | | |
| Time to First COPD Exacerbation | Y | Y | | Y | | | Y | | | | | | | | | |
| On-Treatment COPD Exacerbations ^[3] | | | | Y | | | | | | | | | | | | |
| Post-Treatment COPD Exacerbations ^[3] | | | | Y | | | | | | | | | | | | |

NOTES :

- T = Table, F = Figure, L = Listing, Y = Yes display generated.
- Stats Analysis = Represents TFL related to any formal statistical analyses (i.e. modelling) conducted.
- Summary = Represents TFL related to any summaries (i.e. descriptive statistics) of the observed raw data.
- Individual = Represents FL related to any displays of individual subject observed raw data.
- All the tables will be presented by treatment group.
- [1]: Absolute summary will be done on each at baseline, during each four weeks of treatment and over the entire 24-week treatment period. The change from baseline values will also be summarised by treatment, for each four weeks of treatment and the entire 24-week treatment period.
- [2]: A responder to TDI will be defined as a subject with TDI score of 1 unit or more
- [3]: The number and percentage of subjects reporting 0, 1, 2 or >2 on-treatment COPD exacerbations and the total number of exacerbations will be presented by treatment group. The number and percentage of exacerbations with each outcome category, the number and percentage of exacerbations leading to withdrawal and the number and percentage of exacerbations treated by oral/systemic corticosteroids, antibiotics, or which resulted in a visit to the emergency room or hospitalisation will also be presented. In addition, the exacerbation duration will be summarised.

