8.3.3. Treatment Comparisons

8.3.3.1. Primary Comparisons of Interest

The following treatment comparisons will be performed on trough FEV₁ on Treatment Day 169:

- Umeclidinium 62.5 mcg vs. placebo

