8.3.3.2. Other Comparisons of Interest

The comparisons listed in Section 8.3.3.1 will be performed on the following secondary endpoints:

- Mean TDI focal score at Week 24
- Weighted mean clinic visit FEV₁ over 0 to 6 hours post-dose at Visit 2

The same treatment comparisons will be performed for the other efficacy endpoints.

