Weighted mean clinic visit FEV₁ over 0 to 6 hours post-dose at Visit 2 (Day 1) will be analysed using analysis of covariance (ANCOVA). Treatment group (categorical) will be fitted as the explanatory variable with baseline FEV₁, and country fitted as covariates. Baseline FEV₁ is defined as the mean of the two assessments made pre-dose at Visit2.

Estimated treatment differences for each treatment comparison will be presented together with 95% confidence intervals (CIs) for the difference and p-values.

Secondary endpoints will be analyzed for the Modified Intent-to-treat Population only.

Other Endpoints

Serial FEV₁ at 15mins, 30mins, 1, 3 and 6 hours after dosing will be analysed using a repeated measures model, including baseline FEV1, country, treatment, time, time by treatment interaction and time by baseline interaction fitted as covariates. Baseline FEV1 is defined as the mean of the two assessments made pre-dose at Visit2. This analysis will be performed for Day 1 only.

Time to onset of bronchodilation (defined as an increase of 100 mL in FEV₁ above baseline on Treatment Day 1 (Visit2)) and time to first COPD exacerbation will be compared between treatment groups using Cox's proportional hazards model.

Other endpoints will be analysed for the Modified Intent-to-treat Population only. Full details of the analyses to be performed will be provided in the RAP.

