2. SUMMARY OF KEY PROTOCOL INFORMATION

2.1. Changes to the Protocol Defined Statistical Analysis Plan

There was one change to the originally planned statistical analysis specified in the protocol amendment 03 (Dated: 11-NOV-2015) of study AC4117410 (GSK Document Number [2013N159587_03](#)). This change was made so that primary endpoint description is consistent across all documents.

In the following section of the protocol, the primary endpoint is Clinic visit trough (pre-bronchodilator) FEV₁ on Treatment Day 169.

PROTOCOL SUMMARY

OBJECTIVE(S) and Endpoints (Section 2)

Efficacy (Section 6.2)

Hypotheses (Section 8.1)

Sample Size Assumptions (Section 8.2.1)

In Efficacy Analyses Section (8.3.5.1), it is clarified that the primary endpoint is change from baseline trough in FEV₁ on Day 169.

Actually, the primary endpoint of this study is change from baseline in trough FEV₁ on Day 169. The sample size calculation was based on this endpoint. To avoid any confusion, the primary endpoint has been defined as change from baseline in trough FEV₁ on Day 169 in this RAP.

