2.2. Study Objective(s) and Endpoint(s)

| Objectives | Endpoints |
|---|--|
| Primary Objectives | |
| 
 To evaluate the efficacy of Umeclidinium 62.5 mcg compared with placebo when administrated once-daily via the ELLIPTATM over a 24-week treatment period in subjects with COPD | 
Primary Efficacy Endpoints:
 
 Change from Baseline of Clinic visit trough (pre-bronchodilator) FEV₁ on Treatment Day 169 Trough FEV₁ on Treatment Day 169 is defined as the mean of the FEV₁ values obtained 23 and 24 hours after dosing on Treatment Day 168 (i.e. at Week 24). 
Secondary Efficacy Endpoints:
 
 TDI focal score at Week 24 (Day 168) Weighted mean clinic visit FEV₁ over 0 to 6 hours post-dose at visit 2 (Randomization visit, Day 1) 
Other Efficacy Endpoints:
 
 Trough FEV₁ and TDI focal score at other time points Rescue albuterol/salbutamol use (percentage of rescue-free days and puffs/day) Time to onset (defined as an increase of 100mL above baseline in FEV₁) during 0-6hr post-dose on Treatment Day 1 (Visit 2) Proportion of subjects achieving an increase in FEV₁ of $\geq 12\%$ and $\geq 200\text{mL}$ above baseline at any time during 0 to 6hr post-dose on Treatment Day 1 (Visit 2) |

| Objectives | Endpoints |
|--|--|
| | 
 Proportion of subjects achieving an increase in FEV₁ of ≥100mL above baseline in trough FEV₁ Serial FEV₁ over 0 to 6 hours post-dose (on Day 1) Serial and trough Forced Vital Capacity (FVC) Proportion of responders to TDI. (a responder to TDI will be defined as a subject with TDI score of 1 unit or more) Time to first COPD exacerbation |
| Secondary Objectives | |
| 
 To evaluate the safety of Umeclidinium 62.5 mcg compared with placebo when administrated once-daily via ELLIPTA over a 24-week treatment period in subjects with COPD | 
 Incidence of adverse events Vital signs (pulse rate, systolic and diastolic blood pressure) 12-lead ECG parameters Clinical chemistry and haematology parameters and routine urinalysis |

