| 2.17. | 2.12 | Modified ITT | DB2114634 6.15 | Analysis of Time to Onset (min) (an increase of 100mL in FEV1 above baseline) on Day 1 | | SAC |
| 2.18. | 2.13 | Modified ITT | DB2114634 6.16 | Summary and Analysis of Proportion of Subjects Achieving Increase in FEV1 of $\geq 12\%$ and ≥ 200 mL above Baseline at Any Time during 0-6 h Post-dose on Day 1 | | SAC |
| 2.19. | 2.14 | Modified ITT | DB2114634 6.17 | Summary and Analysis of Proportion of Subjects Achieving Increase in Trough FEV1 of ≥ 100 mL above Baseline | | SAC |
| 2.20. | 2.15 | Modified ITT | DB2114634 6.18 | Summary of Serial FEV1 (L) | | SAC |

| Efficacy: Tables | | | | | | |
|------------------|--------------------|--------------|-------------------------------|---|-------------------|------------------------|
| IMCT No. | China Subgroup No. | Population | IDSL / TST ID / Example Shell | Title | Programming Notes | Deliverable [Priority] |
| 2.21. | 2.16 | Modified ITT | DB2114634 6.19 | Summary of Change from Baseline in Serial FEV1 (L) | | SAC |
| 2.22. | 2.17 | Modified ITT | DB2114634 6.20 | Analysis of Serial FEV1 (L) on Day 1 | | SAC |
| 2.23. | 2.18 | Modified ITT | DB2114634 6.21 | Summary of Baseline FVC (L) | | SAC |
| 2.24. | 2.19 | Modified ITT | DB2114634 6.22 | Summary of Trough FVC (L) | | SAC |
| 2.25. | 2.20 | Modified ITT | DB2114634 6.23 | Analysis of Trough FVC (L) | | SAC |
| 2.26. | 2.21 | Modified ITT | DB2114634 6.24 | Summary of Serial FVC (L) | | SAC |
| 2.27. | 2.22 | Modified ITT | DB2114634 6.25 | Summary of Change from Baseline in Serial FVC (L) | | SAC |
| 2.28. | 2.23 | Modified ITT | DB2114634 6.26 | Analysis of Serial FVC (L) on Day 1 | | SAC |
| 2.29. | 2.24 | Modified ITT | DB2114634 6.27 | Summary of Percentage of Rescue-Free Days | | SAC |
| 2.30. | 2.25 | Modified ITT | DB2114634 6.28 | Summary of Mean Number of Puffs of Rescue Medication per Day | | SAC |
| 2.31. | 2.26 | Modified ITT | DB2114634 6.29 | Analysis of Mean Number of Puffs of Rescue Medication per Day | | SAC |

| Efficacy: Tables | | | | | | |
|------------------|--------------------|--------------|-------------------------------|---|-------------------|------------------------|
| IMCT No. | China Subgroup No. | Population | IDSL / TST ID / Example Shell | Title | Programming Notes | Deliverable [Priority] |
| 2.32. | 2.27 | Modified ITT | DB2114634 6.30 | Summary of BDI Focal Score | | SAC[1] |

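### Percentage of rescue-free days gets only descriptive summaries in the SAP, although the protocol promises a UMEC–placebo comparison, and SAP 2.1 does not record the departure

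*SAP*

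**What the plan says.** Both documents name two rescue measures among the other efficacy endpoints. SAP 2.2, like protocol 6.2.3, has "Rescue albuterol/salbutamol use (percentage of rescue-free days and puffs/day".

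Protocol 8.3.3.1 defines the comparison as "Umeclidinium 62.5 mcg vs. placebo". After applying it to the secondary endpoints, protocol 8.3.3.2 adds: "The same treatment comparisons will be performed for the other efficacy endpoints". On method, protocol 8.3.5.1 says of the other endpoints: "Full details of the analyses to be performed will be provided in the RAP".

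The SAP derives both rescue measures (10.6.5) for a baseline period, six four-week periods and Weeks 1–24. In Table 5 the row "Rescue Salbutamol Use (Percentage of Rescue-Free Days" has nothing in the formal-analysis columns, which the table key explains as "Stats Analysis = Represents TFL related to any formal statistical analyses (i.e. modelling) conducted". Appendix 14 lists a single table for the endpoint, "Summary of Percentage of Rescue-Free Days" (2.29; China 2.24).

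SAP 2.1 states: "There was one change to the originally planned statistical analysis specified in the protocol amendment 03". The change described there is the wording of the primary endpoint as change from baseline.

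**The concern.** The protocol promises a between-arm comparison for this endpoint and the SAP does not plan one. If the SAP is followed as written, the report will show each arm's summary statistics for rescue-free days but no treatment difference or measure of its uncertainty. The other rescue measure, built from the same daily records, will have both.

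There is also a traceability problem. A reader relying on SAP 2.1 for departures from protocol amendment 03 would not learn of this one, and no reason for it appears elsewhere in the SAP. A comparison added after unblinding to fill the gap would be post hoc.

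**Working it through.** No plan figure needs recomputing. The check is a comparison of text.

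**Step 1: the two rescue measures side by side.**

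| Place in the SAP | Rescue-free days | Puffs per day |
|---|---|---|
| 2.2, endpoint list | Listed | Listed |
| 10.6.5, derivation | Yes, including baseline | Yes, including baseline |
| Table 5, formal analysis, absolute value | Blank | Marked |
| Table 5, formal analysis, change from baseline | Blank | Marked |
| Table 5, summaries (absolute and change) | Marked | Marked |
| 7.3.2.4, model | None | ANCOVA: treatment, smoking status, country, baseline |
| Appendix 12, model checking | Not listed | Listed |
| Appendix 14, overall tables | Summary only (2.29) | Summary (2.30) and analysis (2.31) |

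Table 5 has 14 display columns. The rescue-free-days row is marked in columns 4, 7 and 11: summary table, listing, and summary table for change. The formal-analysis columns, 1–3 and 8–10, are empty. The puffs-per-day row directly below is marked in columns 1 and 8. Because 7.3.2.4, Appendix 12 and Appendix 14 show the same pattern, the blanks cannot be put down to a damaged table.

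**Step 2: is this endpoint alone?** The remaining other efficacy endpoints in protocol 6.2.3 all have a model in the SAP:

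- trough FEV1 and TDI at other time points: MMRM (7.1.2, 7.2.2.2)
- time to onset and time to first exacerbation: Cox model (7.3.2.1)
- the 12%/200 mL responders, the 100 mL trough responders and the TDI responders: logistic regression (7.3.2.2)
- serial FEV1, serial FVC and trough FVC: repeated-measures model (7.3.2.3)
- puffs per day: ANCOVA (7.3.2.4)

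Table 5 also has summary-only rows for counts of on- and post-treatment exacerbations, but these are not on the endpoint list. Rescue-free days is therefore the only listed other efficacy endpoint without a model.

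**Step 3: what is missing.** Six four-week periods plus Weeks 1–24 make 6 + 1 = 7 periods. With two populations (overall and China), 7 × 2 = 14 differences would not be estimated.

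**Step 4: would the puffs-per-day model fit?** Only with care. The endpoint is confined to 0–100%. The baseline window in 10.6.5 runs at most from 6 days before Visit 2 to the day of Visit 2, which is 6 + 1 = 7 days. A fully recorded baseline can then take only eight values (0/7 to 7/7). Values may pile up at 0% or 100%, so the normality and constant-variance checks in Appendix 12 could fail.

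**The case against.** The best defence is that the protocol fixes which arms are compared, not how. Its analysis section names no model for either rescue measure, says efficacy data will be summarised descriptively, and leaves the details for other endpoints to the SAP. On that view no specified analysis existed to be changed. This softens the point but does not remove it. The method was delegated; whether to compare was settled in 8.3.3.2. Puffs per day was equally unspecified in the protocol, and the SAP did give it a model.

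Side-by-side summaries might be called a comparison. The SAP's own table key separates modelling from descriptive summaries, and only the former gives a difference with a confidence interval.

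The exploratory status of the endpoint (SAP Appendix 11) does stand and caps the importance of the point. That appendix nevertheless refers to treatment comparisons for the other endpoints, so it presupposes that they are made.

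The objection that a plain ANCOVA may suit a bounded percentage poorly also stands, and the remedy has to allow for it.

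A reader might infer that the endpoint was dropped, or that this is selective analysis. The documents do not support either reading. The endpoint is still listed and derived, and it is summarised by treatment group, both as absolute values and as change from baseline. The summary-only treatment is visible and consistent across the SAP, and the SAP synopsis places all final-analysis decisions before unblinding.

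**Conclusion.** The point holds as a contradiction between protocol and SAP, of minor weight. The protocol commits to a comparison for rescue-free days, the SAP plans by-group description only, and SAP 2.1 does not list the difference. One of two paired rescue measures would have no estimated treatment effect in any of its seven periods, in either population.

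The primary analysis and its conclusion are untouched. No confirmatory claim depends on this endpoint, and puffs per day partly covers the same ground.

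The conclusion assumes that a treatment comparison means an estimated between-arm difference with its uncertainty, which is how the SAP treats every other listed efficacy endpoint. The recommended change also assumes that the data are still blinded.

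**What to change.** Before unblinding, add percentage of rescue-free days to SAP 7.3.2.4, to the formal-analysis columns of Table 5, to Appendix 12 and to Appendix 14, for the overall and China analyses. Use the covariates of the puffs-per-day model (country omitted for China), with the baseline percentage of rescue-free days as the baseline term. Report the treatment difference and 95% CI, with Weeks 1–24 as the main period. Name in advance a fallback suited to a bounded percentage, for example a rank-based comparison, and state that it applies if the residual checks fail.

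The cost is one extra model on variables already derived, one analysis table per population, and a few lines of SAP text. The small downside is one more exploratory comparison without multiplicity adjustment.

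If the sponsor intends the endpoint to be descriptive only, the minimum is an entry in SAP 2.1 recording this as a change from protocol 8.3.3.2, with the reason.
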